## 8.2.3 Follow-up analysis

The evolution of the following aspects will be presented for each one of the follow-up visits of the patients at which the variables listed below are recorded:

- Presence of palmar-plantar erythrodysesthesia: the absolute and relative frequency of patients who as of month 3 of treatment develop palmar-plantar erythrodysesthesia of any grade will be provided. In the sub-population of patients with hand-foot syndrome, the frequency distribution will be presented according to the degree of severity of these AE, according to CTCAE (Common Terminology Criteria form Adverse Event) version 4:
  - o Grade 1
  - o Grade 2

#### o Grade 3

For each one of the evolution visits (month 6 and month 9), a study will be performed to ascertain whether significant changes have occurred in the presence and the grade of the HFS with regard to the previous visit, defined as (improved, maintained or worsened). The Pearson chi-squared test will be used for this purpose (or Fisher's exact test for 2x2 tables or likelihood ratio test for mxn tables, if necessary).

- Presence of fatigue: the absolute and relative frequency of patients with the presence of fatigue of any degree since the baseline visit will be provided. In the sub-population of patients with fatigue, the frequency distribution will be presented according to the degree of severity, according to CTCAE (Common Terminology Criteria form Adverse Event) version 4:
  - o Grade 1
  - o Grade 2
  - o Grade 3
  - o Grade 4

For each one of the evolution visits (month 3, month 6 and month 9), a study will be performed to ascertain whether significant changes have occurred in the grade of fatigue with regard to the previous visit, defined as (improved, maintained or worsened). Significant associations will be sought between the habits of daytime rest, physical aerobic exercise, medication taken, dose and treatment schedule changes, dose interruptions and the number of days of treatment interruption depending on the evolution of the presence and degree of fatigue in the last twelve weeks. The Pearson Chi-squared test will be used for this purpose (or Fisher's exact test for 2x2 tables or likelihood ratio test for mxn tables, if necessary).

- Patient diary data (weekly): the distribution of patient frequencies will be presented according to the following habits:
  - Napping
    - Every day
    - Weekend and/or holidays
    - Sporadically, between 2 or 6 days
    - Has not taken a nap any day

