## • Has taken the medication:

- In the morning (between 7 am and 12 noon)
- In the afternoon (between 1 pm and 7 pm)
- At night (between 8 pm and 6 am)
- I have not taken any medication this week

For each one of the weekly habits described above, a summary calculation will be made (after three months) of each patient's habits in terms of daytime rest, physical exercise and taking their medication, taking the options marked with greater frequency in the last 12 weeks into account.

FACIT\_Fatigue: The main measures of centrality and dispersion measures will be calculated (mean, standard deviation, median, minimum, maximum, IR and 95%CI ) from the score obtained in the FACIT\_Fatigue quality of life scale, calculated as described in ANNEX 1. The absolute and relative frequency of patients with severe fatigue, being those with a score of less than 30 points on the FACIT\_Fatigue scale, will also be presented.

For each one of the evolution visits (week 6, week 12, week 18, week 24, week 30 and week 36), a study will be performed to ascertain whether significant changes have occurred in fatigue-related quality of life versus the previous evaluation, and defined as:

- **Improvement:** if there is an increase of more than 4 points in the FACIT\_Fatigue scale score versus the previous evaluation
- **Maintenance:** if the score on the quality of life scale does not vary by more than 4 points versus the previous evaluation
- **Worsening:** if the score obtained on the Facit\_Fatigue scale decreases by more than four points versus the previous evaluation.

Significant associations will be sought between the habits of daytime rest, the practice of physical aerobic exercise, medication taken, dose and treatment schedule changes, dose interruptions and the number of days of treatment

interruption depending on the evolution in the evaluation of the fatigue in the FACIT\_Fatigue over the last six weeks. The Pearson chi-squared test will be used for this purpose (or Fisher's exact test for 2x2 tables or likelihood ratio test for mxn tables, if necessary).

- Treatment: For each one of the treatment cycles received by patients during the 9-month follow-up, the following will be studied:
  - **Dose change:** the absolute and relative frequency of patients who have changed doses since the last cycle will be provided. In the sub-population of patients with dose changes in the last cycle, their frequency distribution will be presented according to:

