    - Number of dose changes received
      - 1 change \_ New dose
        - Sunitinib 50 mg 4/2 regimen
        - Sunitinib 50 mg 2/1 regimen
        - Sunitinib 37.5 mg 4/2 regimen
        - Sunitinib 37.5 mg 2/1 regimen
        - Sunitinib 25 mg 4/2 regimen
        - Sunitinib 25 mg 2/1 regimen
        - Pazopanib 800 mg/24 hours continuous
        - Pazopanib 400 mg/24 hours continuous
        - Sorafenib 400 mg/24 hours continuous
        - Sorafenib 400 mg/12 hours continuous
      - 2 changes\_ New dose
        - Sunitinib 50 mg 4/2 regimen
        - Sunitinib 50 mg 2/1 regimen
        - Sunitinib 37.5 mg 4/2 regimen
        - Sunitinib 37.5 mg 2/1 regimen
        - Sunitinib 25 mg 4/2 regimen
        - Sunitinib 25 mg 2/1 regimen
        - Pazopanib 800 mg/24 hours continuous
        - Pazopanib 400 mg/24 hours continuous
        - Sorafenib 400 mg/24 hours continuous
        - Sorafenib 400 mg/12 hours continuous
  - **Treatment interruptions:** the absolute and relative frequency of patients who have interrupted the treatment since the last cycle will be given. In

the sub-population of patients with treatment interruptions, their frequency distribution will be presented according to:

- Number of treatment interruptions
  - 1
  - 2
  - 3
  - 4 •
  - 5 •
  - ...
- Total calculation of days of treatment interruption
  - <7 days
  - 7-14 days
  - >14 days

In order to study the evolution of patients in terms of the presence of AEs (HFS and fatigue), patient habits in terms of daytime rest, aerobic physical exercise and taking medication, paired data comparisons will be performed between each one of the visits with the results of the previous visit, as well as of each one of the visits with regard to the results presented at the baseline visit, using, for this purpose, the non-parametric sign tests for categorical variables or the McNemar test in the case of dichotomous variables. In order to ascertain whether there is a significant evolution in the score obtained on the FACIT Fatigue scale throughout the study, comparisons of paired data will be performed for each one of the assessments with regard to the baseline value and with regard to the

previous evaluation using the Student t-test for paired data or the non-parametric Wilcoxon test, as appropriate.

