#### 9 LIST OF TABLES AND TABLE OF CONTENTS

Table/Graph number			Table/Graph title					
1.			Included and evaluable population					
2.			Descriptive analysis					
	.1		Demographic and disease information					
		.1	Age					
		.2	Time from diagnosis and from the advanced diagnosis of the disease					
		.3	Gender					
		.4	ECOG at time of diagnosis, Heng prognostic criteria and site of metastasis					
		.5	Histological type					
		.6	Smoking					
	.2		Dosage and treatment regimen of tyrosine kinase with which the patient begins treatment					
3.			Analysis of evolution					
	.1		Presence of palmar-plantar erythrodysesthesia of any grade (month 3, month 6, month 9)					
		.1	Association between medication intake habits and evolution of hand- foot syndrome (every three months)					
		.2	Association between dose changes and evolution of hand-foot syndrome (every three months)					
		.3	Association between dose, treatment regimen received and the evolution of hand-foot syndrome (every three months)					
		.4	Association between temporary treatment interruptions and evolution of hand-foot syndrome (every three months)					
	.2		Presence of fatigue of any grade (baseline, month 3, month 6, month 9)					
		.1	Association between daytime rest habit and fatigue evolution (every three months)					
		.2	Association between daytime physical exercise and fatigue evolution (every three months)					
		.3	Association between daytime medication-taking habits and fatigue evolution (every three months)					
		.4	Association between daytime dose changes and fatigue evolution (every three months)					
		.5	Association between doses, daytime treatment regimen and fatigue evolution (every three months)					

CT24-GSOP-SD-GL04 NI Study SAP Template; Template Version 1.0, Effective 31-Dec-2013 Page 23 of 29

PFIZER CONFIDENTIAL

	.6	Association between temporary daytime interruptions and fatigue evolution (every three months)
	3	Data from the patient diary
	.1	Daytime rest (weekly)
	.2	Physical exercise (weekly)
	.3	Has taken the medication (weekly)
•-	4	Quality of life (FACIT_Fatigue) (every six weeks)
	.1	Association between daytime habit and evolution on the Facit_Fatigue (every six weeks)
	.2	Association between daytime physical exercise and evolution on the Facit_Fatigue (every six weeks)
	.3	Association between daytime medication-taking habits and evolution on the Facit_Fatigue (every six weeks)

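### FACIT-Fatigue change categories and their association tables refer only to the previous form; a category against baseline should be added beside them

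*SAP*

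**What the plan says.** The FACIT_Fatigue item of SAP 8.2.3 sets the evaluations at "week 6, week 12, week 18, week 24, week 30 and week 36". Improvement is a rise of more than 4 points from the preceding form. Worsening applies when the score on the "scale decreases by more than four points versus the previous evaluation". Maintenance applies "if the score on the quality of life scale does not vary by more than 4 points versus the previous evaluation".

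The same item then looks for associations of napping, exercise, medication taking, dose and schedule changes and interruptions with this evolution "over the last six weeks. The Pearson chi-squared test will be used for this purpose". SAP section 9 lists the matching tables, for example "Association between daytime physical exercise and evolution on the Facit_Fatigue (every six weeks").

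For CTCAE fatigue, SAP 8.2.3 asks at months 3, 6 and 9 whether "changes have occurred in the grade of fatigue with regard to the previous visit, defined as (improved, maintained or worsened"). It relates the same exposures to that evolution over the last twelve weeks.

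Baseline does appear elsewhere. At the end of SAP 8.2.3, for the FACIT score, "comparisons of paired data will be performed for each one of the assessments with regard to the baseline value" and to the previous evaluation, by paired t-test or Wilcoxon test. Fatigue as an adverse event is compared with baseline by sign or McNemar test. The share of patients scoring below 30 is also tabulated. None of these results feeds the change categories or the association tables.

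**The concern.** Secondary objectives 3 and 4 (SAP 2.2) ask what part exercise plays in the onset of fatigue, and how dosing time, napping, breaks and dose reductions bear on its control. An outcome that looks back one form answers a narrower question: did the score move in the last six weeks?

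At week 6 the preceding form is normally the baseline form, so the two questions coincide. From week 12 they separate. A patient who became fatigued early and stayed so gets the same label as one who was never fatigued. If an exposure goes with lasting fatigue, the two exposure groups then have nearly the same mix of labels. A null table could be read as showing that exercise or napping makes no difference, when its outcome could not have shown one.

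**Working it through.** **Inputs.** From the SAP: the cut-off of more than 4 points, the previous-form reference and the six evaluations (8.2.3); a 0–52 range with higher scores better, and below 30 severe (Annex 1); significance at 0.05 (section 4); 100 patients with 5% discontinuation (5.1), so 100 × 0.95 = 95 evaluable. The plan gives no expected frequencies for the categories, so there is no figure of its own to reproduce. The sample size is used only for the 95.

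**Step 1: fixed score paths (no variability assumed).** With score S at form k, the planned rule uses S(k) − S(k−1) and a baseline rule uses S(k) − S(0). Both call worsening below −4 and improvement above +4. W = worsening, M = maintenance, I = improvement.

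| Path, weeks 0 to 36 | Planned rule | Baseline rule | Below 30 |
|---|---|---|---|
| 44, 40, 36, 32, 28, 24, 20 | M M M M M M | M W W W W W | weeks 24, 30, 36 |
| 44, 42, 40, 38, 36, 34, 32 | M M M M M M | M M W W W W | never |
| 44, then 34 throughout | W M M M M M | W W W W W W | never |
| 44, 32, then 37 throughout | W I M M M M | W W W W W W | never |

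The first path is the limit: 6 × 4 = 24 points, or 24/52 = 46% of the scale, with no worsening label. In the fourth, week 12 is an improvement of 37 − 32 = 5 while the patient is 44 − 37 = 7 points below baseline.

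**Step 2: label frequencies with noise.** Assumptions, none from the documents: mean start 40, between-patient SD 8, independent within-patient SD 2 or 4, scores rounded and limited to 0–52. Results are given as SD 2 / SD 4.

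- No true change: about 5% / 19% are called worsening at any form under either rule.
- Lasting 8-point loss by week 6, at each of weeks 12 to 36: planned rule worsening 6% / 21%, barely above the no-change rates; baseline rule 87% / 71%. Of patients more than 4 points below baseline, the planned rule labels 90% / 59% maintenance and 4% / 13% improvement.
- Loss of 2 points per form, at week 36: planned rule worsening 19% / 33%; baseline rule 99% / 90%. Of those worsened against baseline, 80% / 55% are labelled maintenance.

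**Step 3: association tests.** 95 patients were split about 1:1, with loss in the exposed group only. The Pearson chi-square test was applied to the category table at 0.05, with 1,000 runs. Entries are the proportion significant, SD 2 / SD 4.

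| Exposed group | Week | Planned rule | Baseline rule |
|---|---|---|---|
| Lasting 8-point loss | 6 | 1.00 / 1.00 | 1.00 / 1.00 |
| | 12 | 0.05 / 0.06 | 1.00 / 1.00 |
| | 36 | 0.04 / 0.07 | 1.00 / 1.00 |
| 2 points lost per form | 6 | 0.48 / 0.26 | 0.49 / 0.24 |
| | 12 | 0.48 / 0.25 | 1.00 / 0.74 |
| | 36 | 0.51 / 0.25 | 1.00 / 1.00 |

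The rules agree at week 6 apart from simulation error. After that, the planned rule's power against a lasting loss is about the significance level. No attrition beyond 5% is modelled and the effects are large, so only the contrast between rules matters, not the absolute power.

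**The case against.** **The primary objective is protected.** A reader might infer that the study would miss a lasting fall in fatigue-related quality of life. The documents do not support that. The primary objective is descriptive. SAP 8.2.3 summarises the score, tabulates scores below 30, and tests every assessment against baseline. CTCAE fatigue is also tested against baseline. This stands: the gap is confined to the categories and the association tables.

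**The reference is not always on drug.** A reader might also infer that every form from week 12 is compared with an on-treatment form. For sunitinib on schedule that is wrong. Home forms are completed at the start of each cycle with a 7-day recall, and both the 4/2 and 2/1 regimens end in off-treatment time, so the recall week falls off drug. The statement fits only continuous pazopanib and sorafenib. What holds for all three is that the reference is no longer the pre-treatment score.

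**Short-term change suits some exposures.** Suppose a patient falls from 44 to 30, treatment is interrupted, and the score rises to 38. The planned rule records 38 − 30 = +8, improvement. A baseline rule records 38 − 44 = −6, worsening. Fatigue may itself have prompted the interruption, so a baseline-referenced association would be open to reverse causation. This stands, and it is why the planned category should not be replaced.

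**The 24-point path is an extreme.** The background sections put usual onset two to three weeks into treatment and say fatigue tends to ease over cycles. Early onset is caught at week 6. This also stands, but a lasting early loss is the case in which the later tables lose most. The slow-loss argument does not carry over to CTCAE grades, which have no 4-point threshold; there, only the associations lack a baseline version.

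**Conclusion.** The concern holds in limited form. FACIT change categories and all FACIT association tables use only the previous form, and the CTCAE fatigue associations use only the previous visit. After week 6 these tables cannot show associations with lasting fatigue, so they answer objectives 3 and 4 only in part.

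The fixed-path results follow from the SAP's wording alone. The simulated percentages and power rest on assumed starting score, SDs, loss patterns and exposure split; their direction is the same at both SDs tried. The documents do not support calling the planned category the wrong outcome for every exposure, or saying that the descriptive primary result is compromised. This is a worthwhile, cheap improvement to secondary association analyses, not a change the study depends on.

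**What to change.** In SAP 8.2.3, add a second category of improvement, maintenance and worsening at each evaluation, defined against the pre-treatment baseline score with the same 4-point cut-off. In section 9, add association tables that use it for habits and exposures during treatment. Do the same for change in CTCAE fatigue grade from baseline.

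Keep the previous-form category for short-term questions, such as interruptions or dose changes in the last cycle. State that baseline-referenced associations with those exposures may reflect reverse causation. Settle this before the tables are seen, so that the reference is not chosen after the fact.

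Cost: one derived variable per evaluation for each measure, and no new data, since the baseline form is already collected. There are more tables and comparisons. Section 9 lists six FACIT exposures, and week 6 normally needs no second version, so at most 6 × 5 = 30 tests are added. For CTCAE fatigue, six exposures at months 6 and 9 add at most 6 × 2 = 12. Patients without a baseline form cannot be classified.

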6. OBJECTIVES

PRIMARY OBJECTIVE

Fatigue-related quality of life of patients receiving a tyrosine kinase inhibitor evaluated using the validated 13-item FACIT-Fatigue scale for patients with metastatic renal cancer in Spanish.^{1,2}

SECONDARY OBJECTIVES

- 1) Quality of life in patients with palmar-plantar erythrodysaesthesia (hand-foot syndrome).
- 2) To assess the following adverse effects according to version 4 of the CTCAE (Common Terminology Criteria for Adverse Events): any grade of fatigue and HFS.
- 3) To study what role aerobic exercise (walking quickly, running, swimming, playing tennis, dancing and/or riding a bike) plays in the onset of fatigue before starting and during treatment.
- 4) To evaluate what impact the time of drug administration, napping, off-treatment periods, temporary treatment breaks and dose reductions have on controlling fatigue and hand-foot syndrome.
- 5) Time to Treatment Failure (TTF), defined as the time from the start of treatment with a tyrosine kinase inhibitor to tumour progression, treatment discontinuation for any reason or death from any cause.
- 6) Progression-Free Survival (PFS) (median): time from the start of treatment with a tyrosine kinase inhibitor to tumour progression or death from any cause.
- 7) Objective Response Rate according to RECIST version 1.1.

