#### SECONDARY OBJECTIVES

- 1) Quality of life in patients with palmar-plantar erythrodysaesthesia (hand-foot syndrome).
- 2) To assess the following adverse events according to version 4 of the CTCAE (Common Terminology Criteria for Adverse Events): any grade of fatigue and HFS.
- 3) To study what role aerobic exercise (walking quickly, running, swimming, playing tennis, dancing and/or riding a bike) plays in the onset of fatigue before starting and during treatment.
- 4) To evaluate what impact the time of day of drug administration, napping, temporary treatment breaks and dose reductions have on controlling fatigue and hand-foot syndrome.
- 5) Time to Treatment Failure (TTF), defined as the time from the start of treatment with a tyrosine kinase inhibitor to tumour progression, treatment discontinuation for any reason or death from any cause.
- 6) Progression-Free Survival (PFS) (median): time from the start of treatment with a tyrosine kinase inhibitor to tumour progression or death from any cause.
- 7) Objective Response Rate according to RECIST version 1.1.

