#### 8 STATISTICAL ANALYSIS AND METHODOLOGY

#### 8.1 STATISTICAL METHODS

The investigator will collect data from the enrolled patients in an electronic Case Report Form specially designed for this study.

The patient number we provide is a serial number devoid of any identifying value.

The information is stored in an Access database, which in turn is associated with a file, "WorkGroup", detailing the user code and permits of the investigator within the database. People not within this working group cannot access the database.

A Data Management Plan (DMP) will be developed and once approved by the person responsible for the study, the "Queries" will be programmed in the electronic case form so that when the investigator saves the data, it informs him/her of any doubts regarding the data.

All changes made by the investigators during the collection of data will be stored in a table specially designed for this purpose, indicating the user, date, modified field, the old value and the new value.

The fatigue-related quality of life of the patients and the quality of life of patients with palmar-plantar erythrodysaesthesia (hand-foot syndrome) will be studied using the mean, standard deviation and confidence intervals if they follow normal distribution, or the median, minimum, maximum and interquartile range if they do not follow Gaussian distribution. The Wilcoxon test will be used to analyse the inter-visit correlation for patients' quality of life.

The objective response rate according to RECIST version 1.1 will be studied using absolute and relative frequencies.

In order to study the impact of drug administration time, napping, temporary interruptions and dose reductions on fatigue and hand-foot syndrome control, independent samples will be compared using Pearson's chi-square test (or Fisher's exact test for 2x2 tables or likelihood ratio test for mxm tables, if necessary) in the case of qualitative variables and Student's t-test, one-way ANOVA test or non-parametric equivalents, such as the Mann-Whitney U test or Kruskal-Wallis H test in the case of quantitative variables.

The Kaplan-Meier survival estimate will be used to study both the PFS and TTF of patients. The log-rank test will be used to compare the survival distributions.

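### SAP 8.2.3 summarises diary habits over 12 weeks but tests them against six-week FACIT change, and its same-window tables cannot show impact for dose changes, breaks and naps

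*SAP*

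**What the plan says.** **The question.** Secondary objective 4 in SAP 2.2 reads: "To evaluate what impact the time of day of drug administration, napping, temporary treatment breaks and dose reductions have on controlling fatigue" (and hand-foot syndrome). Protocol section 6 asks the same of "temporary treatment breaks and dose reductions have on controlling fatigue and hand-foot syndrome". Objective 3 asks what role aerobic exercise plays in the onset of fatigue. SAP 8.1 introduces its tests with "In order to study the impact of drug administration time, napping, temporary interruptions and dose reductions on fatigue and hand-foot syndrome control".

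**The analysis.** SAP 8.2.3 classes each patient as improved, maintained or worsened against the previous assessment. For FACIT-Fatigue it then says: "Significant associations will be sought between the habits of daytime rest, the practice of physical aerobic exercise, medication taken, dose and treatment schedule changes", plus interruptions and their length, with the change taken "over the last six weeks". The CTCAE fatigue analysis has the same structure but a longer window, ending with "the number of days of treatment interruption depending on the evolution of the presence and degree of fatigue in the last twelve weeks". The tests are Pearson chi-squared, Fisher or likelihood ratio. SAP 8.1 adds t-test, ANOVA and rank tests. None of these is adjusted.

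**The habit summary.** Napping, exercise and time of dosing come from a weekly diary (SAP section 6, Lifestyle). SAP 8.2.3 reduces each to one value per patient after three months, "taking the options marked with greater frequency in the last 12 weeks into account". No other habit summary and no tie rule is given. Yet SAP section 9 lists six-weekly tables such as "Association between daytime habit and evolution on the Facit_Fatigue (every six weeks").

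**The concern.** There are two linked gaps.

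First, exposure and outcome are measured over different periods. A 12-week habit label set against a six-week change can describe a habit the patient did not have for most of that change. Where the label is formed later, it can include weeks after the outcome was recorded. Two analysts could also build different tables from the same text.

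Second, the objectives ask about impact, while the tables place exposure and outcome in the same window with no order between them. If worsening fatigue prompts a dose change, a break or more naps, a neutral or helpful measure can look harmful. If a temporarily poor opening score prompts it, natural recovery can make a neutral measure look helpful. Protocol 7.9 (limitations) mentions unverifiable diary data and the lack of central PFS review, but not this.

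At stake is how secondary objectives 3 and 4 are interpreted. The primary description of FACIT-Fatigue does not use these tables.

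**Working it through.** The plan gives no figure of its own on this point, so the check is a week count and then a reading of the passages side by side.

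**1. Inputs.** FACIT change is assessed at weeks 6, 12, 18, 24, 30 and 36, each against the previous evaluation (SAP 8.2.3). The diary is weekly (SAP section 6). The habit summary covers 12 weeks and is made after three months, taken here as weeks 12, 24 and 36.

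**2. Window count.** The interval ending at week w covers weeks w−5 to w. A summary ending at week w covers weeks w−11 to w.

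| FACIT week | Interval | Three-monthly summary | Summary rolled to that week |
|---|---|---|---|
| 6 | 1–6 | none yet; next (1–12) has 6 in, 6 after | fewer than 12 weeks exist |
| 12 | 7–12 | 1–12: 6 before, 6 in | same |
| 18 | 13–18 | last (1–12) has 0 in; next (13–24) has 6 in, 6 after | 7–18: 6 before, 6 in |
| 24 | 19–24 | 13–24: 6 before, 6 in | same |
| 30 | 25–30 | last (13–24) has 0 in; next (25–36) has 6 in, 6 after | 19–30: 6 before, 6 in |
| 36 | 31–36 | 25–36: 6 before, 6 in | same |

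On either reading, no 12-week summary has more than 6 of its 12 weeks inside the FACIT interval.

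**3. Effect on one patient.** Assume a complete diary, two options, at least six weeks on the old habit, and one clean switch m weeks into the interval. A summary ending with the interval holds 6+m old weeks and 6−m new weeks.
- m = 0: 6 v 6, a tie with no rule, although all 6 interval weeks are under the new habit.
- m = 1: 7 v 5, old label, although 5 of the 6 interval weeks are under the new habit.
- m = 2: 8 v 4, old label, although 4 of the 6 are under the new habit.

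The error reverses if weeks 18 and 30 use the next summary. That summary holds m old weeks and 12−m new weeks. At m = 5 it gives the new label (5 v 7) although 5 of the 6 interval weeks were under the old habit.

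**4. Direction of cause.** Protocol section 5, repeated in SAP section 2, reports that half the patients in the pivotal sunitinib trial had their dose cut to control adverse effects. It also says that fatigue leads to repeated interruptions and that asthenia went with more daytime napping. SAP 8.2.3 counts dose changes and interruptions since the last cycle and sets no order between them and the FACIT change. For these three exposures an association could arise in either direction.

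**5. Illustration only; every input is assumed.** A simulation of the six-week chi-squared table used zero true effect, 60 or 95 patients, between-patient SD 8, within-patient SD 7, weekly autocorrelation 0.8 or 0.9, measurement SD 3 and 1,500 runs per setting. Exposure became more likely after a fall of more than 4 points in the first three weeks of the interval.

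| Exposure probability without / with the fall | Tables with p<0.05 |
|---|---|
| 0.20 / 0.20 (no trigger) | 4–5% |
| 0.10 / 0.30 | 8–11% |
| 0.10 / 0.50 | 18–27% |
| 0.05 / 0.50 | 25–38% |

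This shows that the mechanism can operate. It does not estimate its size in this study.

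**The case against.** **Already descriptive.** The study is called descriptive, and SAP 8.2.3 and its table titles already speak of associations. That is fair. The remaining gap is that objective 4 and SAP 8.1 say impact and nothing states how far the tables answer it.

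**Under-specified rather than contradictory.** No sentence says the 12-week summary feeds the FACIT tables, and it fits the 12-week CTCAE tables well. An analyst could tabulate the weekly diary over six weeks. This also stands in part, but the 12-week rule is the only one written, so the FACIT tables need either that rule or one invented later.

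**Stronger readings a reader might infer, which the documents do not support:**
- *That prior fatigue is ignored.* The outcome is already change from the previous evaluation.
- *That the tables will make these measures look harmful, at a known error rate.* The documents give neither exposure rates per window nor the timing of worsening relative to exposure, and bias can run the other way. High rates are also doubtful for dose changes and breaks: 30% exposed per window, independent over six windows, implies 1 − 0.7⁶ = 88% ever exposed. In the pivotal sunitinib trial 38% interrupted treatment and 50% reduced the dose.
- *That dosing time and exercise share the problem.* The documents describe no reverse path for either.
- *That a lagged model is required.* Adjusting for the score at the end of the exposure interval removes benefit already obtained. Omitting that score can keep the reverse-causation bias. Neither version settles objective 4.

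**Conclusion.** The concern holds in two limited parts.

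The window mismatch follows from the SAP text, taking three months as 12 weeks. There is no habit value at week 6. At weeks 12, 24 and 36 half of the summary precedes the outcome interval. At weeks 18 and 30 half lies after it, or before it if the summary is rolled forward. The mislabelling after one or two weeks also rests on the clean-switch assumptions in the working. How many patients switch habits is unknown.

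The interpretive gap covers dose changes, interruptions and naps, where the documents themselves supply the reverse path. These tables cannot separate cause from consequence there, and neither the size nor the direction of any bias can be derived from the documents.

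Both parts should be corrected before analysis, but they concern secondary objectives 3 and 4 only.

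**What to change.** 1. **SAP 8.2.3, habit summary.** For the FACIT tables, summarise each weekly diary habit over the six weeks since the previous FACIT assessment, and state a tie rule. Keep the 12-week summary for the 12-week CTCAE tables.
2. **SAP 8.1 and 8.2.3, wording.** Replace impact with association in 8.1, and state that the 8.2.3 tables are not evidence of impact. Add reverse causation for dose changes, interruptions and naps to the limitations, which at present appear only in Protocol 7.9.

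The data are already collected, so the cost is text and a little more tabulation. A six-week summary uses fewer diary weeks, so ties will be more common: a switch three weeks into the interval gives 3 v 3. The conclusion for objective 4 becomes more modest. A lagged model may be added as an exploratory analysis, with its biases stated, but it is optional.
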